9 STATISTICAL ANALYSIS PLAN

This section outlines the statistical analysis strategy and procedures for the study. Changes to analyses made after the protocol has been finalized, but prior to final database lock, will be documented in a supplemental statistical analysis plan (sSAP) and referenced in the Clinical Study Report (CSR) for the study. Post hoc exploratory analyses will be clearly identified in the CSR.

9.1 Statistical Analysis Plan Summary

Study Design Overview	A phase 3, open-label clinical study to evaluate the immunogenicity and safety of 9vHPV vaccine, in Japanese 9-15 boys and 9-14 girls of age		
Treatment Assignment	Approximately 300 participants will be enrolled and allocated in a 1:1:1 ratio based on gender and age into the 3-dose [0,2,6 regimen] in 9 to 15 years old boys, 2-dose [0,6 regimen] in 9 to 14 years old boys and 2-dose [0,6 regimen] in 9 to 14 years old girls arms. Details are provided in Section 6.3.1.		
Analysis Populations	Immunogenicity: Per-Protocol Immunogenicity (PPI) population Safety: All Participants as Treated (APaT) population		
Primary Endpoint(s)	 Seroconversion to each of HPV 6, 11, 16, 18, 31, 33, 45, 52 and 58 at 1 month post last dose (Month 7) following 3 doses of the 9vHPV vaccine. Seroconversion to each of HPV 6, 11, 16, 18, 31, 33, 45, 52 and 58 at 1 month post last dose (Month 7) following 2 doses of the 9vHPV vaccine. 		
Key Secondary Endpoints	 Geometric mean titers (GMTs) to each of HPV 6, 11, 16, 18, 31, 33, 45, 52 and 58 at 1 month post last dose (Month 7) following 3 doses of the 9vHPV vaccine. GMTs to each of HPV 6, 11, 16, 18, 31, 33, 45, 52 and 58 at 1 month post last dose (Month 7) following 2 doses of the 9vHPV vaccine. 		
Statistical Methods for Key Immunogenicity Analyses	The primary immunogenicity objective is estimation of the HPV 6, 11, 16, 18, 31, 33, 45, 52 and 58 seroconversion at 1 month post last dose (Month 7) following 3 doses and 2 doses of the 9vHPV vaccine. Seroconversion to a specific HPV type is defined as changing serostatus from seronegative at Day 1 to seropositive at 1 month post last dose (Month 7). Percent seroconversion will be evaluated by computing point estimates and constructing 95% confidence interval (CI) of the percent of participants who seroconvert at 1 month post last dose (Month 7). Calculation of the 95% CI of percent seroconversion is based on the exact binomial method proposed by Clopper and Pearson [Clopper, C. J. and Pearson, E. S. 1934]. The secondary objective is to estimate GMTs at 1 month post last dose (Month 7) for each of HPV 6, 11, 16, 18, 31, 33, 45, 52, and 58 following 3 doses and 2 doses of the 9vHPV vaccine. GMTs and corresponding 95% CI will be derived by taking the anti-logarithm of the mean and corresponding 95% CI of the mean of the log-transformed anti-HPV titers.		

Statistical Methods for Key Safety Analyses	Incidence of solicited injection-site AEs, systemic AEs, SAEs, and serious vaccine-related AEs will be summarized by study arm.
Interim Analyses	No interim analyses are planned in this study.
Multiplicity	Not applicable. The study is an estimation-only study.
Sample Size and Power	The study will enroll 300 participants (100 participants for each study arm) to receive V503. At least 95 participants evaluable per study arm will allow estimation of percent seroconversion that has a corresponding 95% CI with a half-width of about 3 percentage points, assuming true percent seroconversion of 99% and the discontinuation rate and exclusion from the HPV type-specific PPI population of at most 5%. In addition, at least 95 participants evaluable per study arm provides at least 0.99 probability to demonstrate that the point estimate of the percent seroconversion exceeds 90% for all of the 9 HPV types when the true percent seroconversion is 99%. At least 95 participants evaluable per study arm provides at least 0.88 probability to attain a lower limit of 95% CI of percent seroconversion equal to or more than 90% when the true percent seroconversion is at least 99%.

9.2 Responsibility for Analyses/In-house Blinding

The statistical analysis of the data obtained from this study will be the responsibility of the designee/Clinical Biostatistics department of the Sponsor. This trial is being conducted as an open-label study, i.e., participants, investigators, and Sponsor personnel will be aware of participant treatment assignments after each participant is enrolled and treatment is assigned.

First database lock will be executed when all girls aged 9 to 14 years old in the 2-dose arm have either completed the Month 7 visit (1 month post last dose) or discontinued from the study before that time to report on base phase analysis for this arm.

A second database lock will be executed at end-of-study to report on base phase analysis for the 2-dose and 3-dose arms in boys and on extension phase analysis for all study arms for safety and persistence of immune response.

Summaries of the primary and secondary immunogenicity endpoints will be reported in Integrated Summary of Immunogenicity reports where in addition to reporting the immunogenicity results in this study, the study results will be compared with immunogenicity results in studies of 16 to 26 year-old Japanese males and females who received 3 doses of the 9vHPV vaccine for the purpose of immunobridging efficacy in 16 to 26 year-old Japanese males and females to 9 to 15 year-old Japanese boys and girls. The results of the 2-dose arm in girls and the 2-dose and 3-dose arms in boys will be reported in two separate integrated Summary of Immunogenicity reports. The details about the analysis will be documented in a separate iSAP.

9.3 Hypotheses/Estimation

Objectives of the study are stated in Section 3. The study is an estimation-only study. No hypothesis will be tested.

9.4 Analysis Endpoints

9.4.1 Immunogenicity Endpoints

The primary immunogenicity endpoints are seroconversion to HPV 6, 11, 16, 18, 31, 33, 45, 52 and 58 at 1 month post last dose (Month 7) following 3 doses; and following 2 doses of the 9vHPV vaccine. Seroconversion is defined as changing serostatus from seronegative at Day 1 to seropositive at 1 month post last dose (Month 7). A participant with a cLIA titer at or above the serostatus cutoff for a given HPV type is considered seropositive for that HPV type.

The key secondary immunogenicity endpoints are cLIA geometric mean titers (GMTs) for anti-HPV 6, 11, 16, 18, 31, 33, 45, 52 and 58 at 1 month post last dose (Month 7) following 3 doses; and following 2 doses of the 9vHPV vaccine. Exploratory endpoints include cLIA GMTs and seropositivity for each vaccine HPV type at Months 18 and 30 to assess persistence of immune responses.

9.4.2 Safety Endpoints

- Solicited injection-site AEs and elevated temperatures Days 1 through 5 post vaccination
- Systemic AEs, SAEs and Serious vaccine-related AEs Days 1 through 15 post vaccination
- SAEs and Serious vaccine-related AEs observed any time during the study

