4 STUDY DESIGN

4.1 Overall Design

V503-066-02 FINAL PROTOCOL

This is a phase 3 open-label study to evaluate the immunogenicity and safety of a 9vHPV (types 6, 11, 16, 18, 31, 33, 45, 52, and 58) vaccine (V503) in Japanese boys and girls aged 9 to 15 years. This study will consist of two periods. Period I of the study is to evaluate the immunogenicity and safety/tolerability of the 9vHPV vaccine up to the time point of Month 7. Period II of the study is to evaluate the long-term immunogenicity and safety from Month 7 to Month 30. Analysis of the base phase (Period I) for the 2-dose arm in girls aged 9 to 14 years old is planned to be conducted when all girl participants have completed their Period I (Month 7 visit) or discontinued from study before that time. Analysis of the base phase (Period I) for the 2-dose and 3-dose arms in boys and extension phase (Period II) for all arms will be conducted at the end of study.

This study will enroll approximately 300 Japanese boys and girls in total, and approximately 100 participants will be allocated to each of the following three arms:

31

- 3-dose (Day 1, Month 2 and Month 6) in boys aged 9 to 15 years
- 2-dose (Day 1 and Month 6) in boys aged 9 to 14 years
- 2-dose (Day 1 and Month 6) in girls aged 9 to 14 years

Enrollment of the girl cohort will be initiated first. Enrollment of the boy cohorts will be initiated at a later time to be determined by the Sponsor.

Blood samples will be collected on Day 1 immediately before vaccination, and subsequently Month 7, Month 18 and Month 30 to evaluate HPV antibody responses.

Participants will be followed for injection-site AEs and systemic AEs from Day 1 through Day 15 following each vaccination. SAEs will be recorded regardless of causality from the time of allocation/randomization through 6 months post last dose. Vaccine-related SAEs and deaths will be collected throughout the study. New medical conditions (defined as incident medical conditions occurring outside of a Days 1 to Days 15 period following each vaccination and not considered SAEs) will be recorded for all participants at each study visit throughout the study.

Specific procedures to be performed during the study, as well as their prescribed times and associated visit windows, are outlined in the SoA in Section 1.3. Details of each procedure are provided in Section 8.

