8.3.4 Vaccination Report Card

The investigator or delegate will train the participant's legally acceptable representative in the use of the VRC at Visit 1 (Day 1). Temperatures, injection-site reactions, other complaints or illnesses, and concomitant medications or vaccinations will be recorded on the VRC by the participant's legally acceptable representative. The participant's legally acceptable representative should be informed to contact the investigator immediately in the event of a hospitalization or visit to another physician.

The participant's legally acceptable representative will use the VRC to document the following information:

- Oral temperatures measured from Day 1 (day of vaccination) through Day 5 postvaccination.
 - Participant's legally acceptable representative will record participant's oral temperature in the evening after each study vaccination and daily, at the same time of day, for 4 days after each study vaccination for the purpose of identifying febrile events
 - Note: If an oral temperature indicates a fever (defined as an oral temperature of ≥37.5°C), the AE of "fever" must be documented in the appropriate eCRF
- Solicited injection-site AEs (redness/erythema, swelling, and tenderness/pain) from Day 1 through Day 5 postvaccination
- Injection-site and systemic AEs from Day 1 through Day 15 postvaccination
- Concomitant medications and non-study vaccinations from Day 1 through Day 15 postvaccination

In order to ensure that the VRC is being filled out without delay, telephone contacts to remind the participant's legally acceptable representative will be conducted after 15 days postvaccination.

V503-066-02 FINAL PROTOCOL

PROTOCOL/AMENDMENT NO.: 066-02

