8.4 Adverse Events, Serious Adverse Events, and Other Reportable Safety Events

The definitions of an AE or SAE, as well as the method of recording, evaluating, and assessing causality of AE and SAE and the procedures for completing and transmitting AE, SAE, and other reportable safety event reports can be found in Appendix 3.

Adverse events, SAEs, and other reportable safety events will be reported by the participant (or, when appropriate, by a caregiver, surrogate, or the participant's legally authorized representative).

The investigator and any designees are responsible for detecting, documenting, and reporting events that meet the definition of an AE or SAE as well as other reportable safety events. Investigators remain responsible for following up AEs, SAEs, and other reportable safety events for outcome according to Section 8.4.3.

The investigator, who is a qualified physician, will assess events that meet the definition of an AE or SAE as well as other reportable safety events with respect to seriousness, intensity and causality.

8.4.1 Time Period and Frequency for Collecting AE, SAE, and Other Reportable Safety Event Information

All AEs, SAEs, and other reportable safety events that occur after the participant's legally acceptable representative provides documented informed consent but before allocation/randomization must be reported by the investigator if they cause the participant to be excluded from the study, or are the result of a protocol-specified intervention, including but not limited to washout or discontinuation of usual therapy, diet, placebo, or a procedure.

From the time of allocation/randomization through 14 days following the first vaccination(s) and from the time of any subsequent vaccination(s) through 14 days thereafter, all AEs, SAEs, and other reportable safety events must be reported by the investigator. All SAEs and other reportable safety events that occur from the time of allocation/randomization through 6 months following the last vaccination must be reported by the investigator, regardless of whether the events are considered to be vaccine-related by the investigator.

Additionally, any SAE brought to the attention of an investigator at any time outside of the time period specified in the previous paragraph also must be reported immediately to the Sponsor if the event is either:

- A death that occurs prior to the participant completing the study, but outside the time period specified in the previous paragraph.

OR

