9.6.2 Statistical Methods for Safety Analyses

Safety and tolerability will be assessed by clinical review of all relevant parameters including adverse events (AEs).

The analysis of safety results usually follows a tiered approach in the studies conducted by the Sponsor. However, this study has no comparison between study arms. Thus, the following summaries will be provided as described in Table 8.

- Incidence is defined as (number of participants with the indicated endpoint divided by the total number of participants with follow-up over the relevant period)*100%.

- For the measured adverse events of redness and swelling, 0 to 1 inch will be categorized as mild intensity, >1 inch to 2 inches will be categorized as moderate intensity, and >2 inches will be categorized as severe intensity.

The specific events of interest in this study will be injection-site prompted adverse events on the VRC, such as pain/tenderness, swelling and redness/erythema occurring Day 1 through 5 following any vaccination, and elevated temperature (≥37.5°C), from Day 1 through 5 following any vaccination.

Table 8 Analysis Strategy for Safety Parameters

		Follow-Up	Period	
		After Any	Vaccination Visit	
	Within			
	study			Any Time
	arm	Day 1	Day 1	During
Adverse Event Endpoint	95%CI [∥]	to Day 5 [†]	to Day 15 [†]	Study
Clinical AEs/vaccine-related AEs				
Any AEs/vaccine-related AEs			•	
Deaths				•
Injection-site AEs/vaccine-related AEs				
Injection-site AEs/vaccine-related AEs of pain/tenderness,	•	•		
swelling, and redness/erythema	•	•		
Other injection-site AEs/vaccine-related AEs				
Severe injection-site AEs§/vaccine-related AEs	•	•		
Number (%) of participants by maximum intensity rating,		•		
over all injection-site AEs§/vaccine-related AEs				
Number (%) of participants by maximum intensity rating,		•		
within each of the categories of injection-site AEs [§] /vaccine-related				
AEs				
Systemic AEs/vaccine-related AEs	ı		_	1
Any systemic AEs/vaccine-related AEs	•		•	
Number (%) of participants by maximum intensity rating,			•	
over all systemic AEs/vaccine-related AEs				
Temperatures	ı	1	_	1
Elevated temperatures#	•	•		
Maximum temperatures ^{††}		•		
AEs of Special Interest				
Serious AEs	•		•	•
Serious vaccine-related AEs	•		•	•
New medical conditions ^{‡‡}				•
Pregnancy outcomes				•
Pregnancy outcomes				•

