10.3.4 Recording AE and SAE

AE and SAE recording

- When an AE/SAE occurs, it is the responsibility of the investigator to review all documentation (eg, hospital progress notes, laboratory, and diagnostics reports) related to the event.
- The investigator will record all relevant AE/SAE information on the AE CRFs/worksheets at each examination.
- It is not acceptable for the investigator to send photocopies of the participant's medical records to the Sponsor in lieu of completion of the AE CRF page.
- There may be instances when copies of medical records for certain cases are requested by the Sponsor. In this case, all participant identifiers, with the exception of the participant

number, will be blinded on the copies of the medical records before submission to the Sponsor.

• The investigator will attempt to establish a diagnosis of the event based on signs, symptoms, and/or other clinical information. In such cases, the diagnosis (not the individual signs/symptoms) will be documented as the AE/SAE.

Assessment of intensity

- An event is defined as "serious" when it meets at least 1 of the predefined outcomes as described in the definition of an SAE, not when it is rated as severe.
- The investigator will make an assessment of intensity for each AE and SAE (and other reportable safety event) reported during the study and assign it to 1 of the following categories:
 - Mild: An event that is easily tolerated by the participant, causing minimal discomfort and not interfering with everyday activities (for pediatric studies, awareness of symptoms, but easily tolerated).
 - Moderate: An event that causes sufficient discomfort to interfere with normal everyday activities (for pediatric studies definitely acting like something is wrong).
 - Severe: An event that prevents normal everyday activities. An AE that is assessed as severe should not be confused with an SAE. Severe is a category utilized for rating the intensity of an event; and both AE and SAE can be assessed as severe (for pediatric studies, extremely distressed or unable to do usual activities).
- Injection site erythema/redness or swelling from the day of vaccination through Day 5 postvaccination will be evaluated by maximum size.

Assessment of causality

- Did the Sponsor's product cause the AE?

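### Injection-site AEs are recorded to Day 15, but Table 8's injection-site severity rows stop at Day 5, so a severe, non-serious event starting on Days 6–15 enters none of them

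*Combined protocol and SAP*

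**What the plan says.** **Collection.** Section 4.1 states: "Participants will be followed for injection-site AEs and systemic AEs from Day 1 through Day 15 following each vaccination". The Vaccination Report Card (Section 8.3.4) has two windows. A short one covers the prompted reactions: "Solicited injection-site AEs (redness/erythema, swelling, and tenderness/pain) from Day 1 through Day 5 postvaccination". A longer one covers everything else: "Injection-site and systemic AEs from Day 1 through Day 15 postvaccination". Section 8.4.1 sets the same outer limit for the investigator: "from the time of any subsequent vaccination(s) through 14 days thereafter, all AEs, SAEs, and other reportable safety events must be reported".

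**Grading.** Appendix 3 (Section 10.3.4) does not tie intensity to a window: "The investigator will make an assessment of intensity for each AE and SAE". It limits only the size measurement to the early days: "Injection site erythema/redness or swelling from the day of vaccination through Day 5 postvaccination will be evaluated by maximum size".

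**Analysis.** Section 9.4.2 lists "Solicited injection-site AEs and elevated temperatures Days 1 through 5 post vaccination". Its Day 1–15 line names systemic AEs and serious AEs, not injection-site AEs. Table 8 (Section 9.6.2) has one row for severe injection-site AEs, with a 95% CI. It also has three rows that begin "Number (%) of participants by maximum intensity rating": over all injection-site AEs, within each injection-site category, and over all systemic AEs. The severe row and the first two intensity rows are marked for Day 1 to Day 5. The systemic intensity row is marked for Day 1 to Day 15.

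**The concern.** The injection-site severity rows are not labelled as solicited events, and one is worded as covering all injection-site AEs. A reader of the study report would take that row to summarise everything recorded, when it covers only the first third of the recording period. Systemic AEs, collected on the same card over the same 15 days, do get an intensity summary for the whole period. Safety and tolerability is a primary objective. For late-onset injection-site AEs the report would have the grades in the database but no table that shows them.

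**Working it through.** **Step 1. Are late events recorded and graded?** Yes. Sections 4.1 and 8.3.4 run to Day 15. Section 8.4.1 runs to 14 days after a dose, which the Table 8 footnote equates with Day 15. Section 10.3.4 requires an intensity for each AE. A severe injection-site AE with onset on Day 7 would be in the data with its grade.

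**Step 2. Which windows does Table 8 apply?** The table reached the reader through text extraction, so I matched each mark to a column by position and checked the match on rows whose window is fixed elsewhere.

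| Table 8 row | Marks read | Independent check |
|---|---|---|
| Elevated temperatures | 95% CI, Day 1–5 | Agrees with Section 9.4.2 |
| Any systemic AEs | 95% CI, Day 1–15 | Agrees with Section 9.4.2 |
| Deaths | Any time | Agrees with Section 4.1 (collected throughout) |
| Any AEs | Day 1–15 | – |
| Severe injection-site AEs | 95% CI, Day 1–5 | – |
| Maximum intensity, all injection-site AEs | Day 1–5 | – |
| Maximum intensity, each injection-site category | Day 1–5 | – |
| Maximum intensity, systemic AEs | Day 1–15 | – |
| Other injection-site AEs | no mark legible | – |

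The rows that can be checked fall where they should, which supports the reading of the three injection-site severity rows.

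**Step 3. Follow one event.** Take a severe, non-serious injection-site AE with onset on Day 7.

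- Severe injection-site row: not counted (Day 1–5).
- Both injection-site maximum-intensity rows: not counted (Day 1–5).
- Any AEs: counted, without intensity (Day 1–15).
- Other injection-site AEs: possibly counted; the window cannot be read, and the row carries no intensity.
- Serious AE rows: not counted, because severe is not the same as serious (Section 10.3.4). A serious event would be counted there.

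**Step 4. Share of the window.** The severity rows cover 5 of 15 days, so 15 − 5 = 10 days (10/15 = 67%) lie outside them. This is a share of days, not of events.

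**Step 5. Scale.** The counts here are assumed, since the documents give no late-onset rate. With n = 100 per arm (Section 9.9) and the plan's Clopper–Pearson method, the limits are L = Beta⁻¹(0.025; x, n − x + 1) and U = Beta⁻¹(0.975; x + 1, n − x).

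Table 9 reproduces first:

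- x = 1: (5.45 − 0.03)/2 = 2.71, stated 2.7.
- x = 2: (7.04 − 0.24)/2 = 3.40, stated 3.4.

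For x = 0, L = 0 and U = 1 − 0.025^(1/100) = 3.6%. Then:

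| Severe, onset Days 1–5 | Severe, onset Days 6–15 (other participants) | Table 8 as planned | Day 1–15 summary |
|---|---|---|---|
| 0 | 1 | 0/100 (0 to 3.6%) | 1/100 (0.03 to 5.45%) |
| 0 | 2 | 0/100 (0 to 3.6%) | 2/100 (0.24 to 7.04%) |

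If the window refers to onset, extending it can add participants with a severe event and cannot remove any, so the count can only stay the same or rise.

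**The case against.** The best defence is that Day 5 is deliberate. Section 3 names solicited injection-site AEs as the endpoint, solicitation on the card ends at Day 5, redness and swelling are sized only to Day 5, Section 9.6.2 calls the prompted Day 1–5 reactions the events of specific interest, and Section 4.2.1.2 says the safety assessments match earlier studies. This stands for the solicited events, and a reader who inferred that the Day 5 limit is itself an error would be going beyond the documents. It does not explain why injection-site AEs recorded and graded after Day 5 have no severity summary when systemic AEs do, or why one row is worded as covering all injection-site AEs.

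Three other objections also have force.

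- **Worsening.** A reader might infer that a reaction starting on Day 4 and becoming severe on Day 8 is also left out. The documents do not say so. Table 8 does not state whether its window applies to onset or to the day of peak intensity. If it applies to onset, that reaction could be counted at its maximum grade. The case is undefined, not excluded.
- **Loss of the event.** A reader might infer that late severe events disappear from the report. They do not, as Step 3 shows, and Section 9.6.2 also provides for clinical review of the AEs.
- **Damaged table.** One row in the same block has no legible mark, so a second lost mark elsewhere cannot be fully excluded. The checks in Step 2 make that unlikely.

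**Conclusion.** The point holds in a limited form. As Table 8 reads, a severe, non-serious injection-site AE with onset on Days 6–15 enters no injection-site severity row, although the event and its grade are in the database. The 67% of days outside the rows should not be read as 67% of severe reactions; with no late-onset rate in the documents, the number affected may be small or zero. If events do occur, the change is of the order shown in Step 5: one or two participants per arm of 100, moving an estimate of 0% to 1% or 2%. The conclusion rests on the column reading of Table 8 and on the window referring to onset, which the plan should state. It is a cheap improvement to completeness and does not call the Section 3 safety endpoint into question.

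**What to change.** 1. Keep the Day 1–5 severity rows in Table 8 and label them as the solicited-event analysis, so that comparability with earlier studies is preserved.
2. Add a supplementary Day 1–15 summary for severe injection-site AEs and for maximum intensity over all injection-site AEs.
3. State that the window applies to the onset of the AE and that the AE's maximum intensity is used. This also settles reactions that worsen after Day 5.
4. State the window for the row on other injection-site AEs if the source table does not already show it.

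The Section 3 endpoint needs no change. Section 9 allows such changes through a supplemental SAP before final database lock. Section 9.2 plans a first lock for the girls' arm, so the change would have to be in place by then to serve that report.

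**Cost.** A few lines of text and one more column, with no new data. There are two downsides. Redness and swelling are graded by size through Day 5 and by the Appendix 3 scale afterwards, so the Day 1–15 rows mix two gradings and need a footnote saying so. The severity figures may also come out slightly less favourable.

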
 An SAE that is considered by an investigator, who is a qualified physician, to be vaccine related.

Investigators are not obligated to actively seek AEs or SAEs or other reportable safety events in former study participants. However, if the investigator learns of any SAE, including a death, at any time after a participant has been discharged from the study, and he/she considers the event to be reasonably related to the study intervention or study participation, the investigator must promptly notify the Sponsor.

All initial and follow-up AEs, SAEs, and other reportable safety events will be recorded and reported to the Sponsor or designee within the time frames as indicated in Table 4.

Table 4 Reporting Time Periods and Time Frames for Adverse Events and Other Reportable Safety Events

Type of Event	Reporting Time Period: Consent to Randomization/ Allocation	Reporting Time Period: Randomization/ Allocation through Protocol-specified Follow-up Period	Reporting Time Period: After the Protocol- specified Follow-up Period	Time Frame to Report Event and Follow-up Information to Sponsor:
NSAE	Report if: - due to protocol- specified intervention - causes exclusion - participant is receiving placebo run- in or other run-in treatment	Report all	Not required	Per data entry guidelines
SAE	Report if: - due to protocol- specified intervention - causes exclusion - participant is receiving placebo run- in or other run-in treatment	Report all	Report if: - drug/vaccine related any death until participant completion of study (Follow ongoing to outcome)	Within 24 hours of learning of event
Pregnancy/ Lactation Exposure	Report if: - participant has been exposed to any protocol-specified intervention (eg, procedure, washout or run-in treatment including placebo run-in)	Report all	Previously reported - Follow to completion/ termination; report outcome	Within 24 hours of learning of event
Cancer	Report if: - due to intervention - causes exclusion	Report all	Not required	Within 5 calendar days of learning of event (unless serious)
Overdose	Report if: - receiving placebo run- in or other run-in medication	Report all	Not required	Within 5 calendar days of learning of event

NSAE=nonserious adverse event; SAE=serious adverse event

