9.5.2 Safety Analysis Population

Safety analyses will be conducted in the APaT population, which consists of all participants who received at least 1 dose of 9vHPV vaccine and have provided safety data at any time during the study. Participants will be included in the study arm corresponding to the study treatment they actually received for the analysis of safety data using the APaT population (i.e., 3 doses [0,2,6 regimen] or 2 doses [0,6 regimen] of 9vHPV vaccine). For participants who received only 1 dose of 9vHPV vaccine, or a participant allocated to the 3-dose regimen arm but received 2 doses that does not correspond to the [0,6 regimen], a safety profile listing will be created separately from the safety reports that will be provided for the 3-dose [0,2,6 regimen] and 2-dose [0,6 regimen] arms.

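### The all-cause SAE summary is planned for the whole study (to Month 30), but SAEs regardless of causality are collected only to 6 months after the last dose (about Month 12)

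*Combined protocol and SAP*

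**What the plan says.** **Analysis.** Section 9.4.2 names the endpoint "SAEs and Serious vaccine-related AEs observed any time during the study", with all-cause SAEs listed separately from vaccine-related ones. In Table 8 (Section 9.6.2) the Serious AEs row is marked for the Day 1 to 15 period, for the whole-study period and for a within-arm 95% CI. No footnote limits the window or ties the CI to one period.

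**Collection.** Section 4.1 states that "SAEs will be recorded regardless of causality from the time of allocation/randomization through 6 months post last dose" and then that "Vaccine-related SAEs and deaths will be collected throughout the study". Section 8.4.1 gives the same limit: "All SAEs and other reportable safety events that occur from the time of allocation/randomization through 6 months following the last vaccination must be reported". Outside that window it requires only deaths before study completion and SAEs judged vaccine-related. Table 4 places "any death until participant completion of study" in the column for events after the protocol-specified follow-up period.

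**Reporting.** Section 4.1 says "Period II of the study is to evaluate the long-term immunogenicity and safety from Month 7 to Month 30". Section 9.2 has the second database lock report "on extension phase analysis for all study arms for safety and persistence of immune response".

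**The concern.** The summary period and the collection period for the same events differ by about 18 months. The numerator of the Serious AEs row follows one rule to about Month 12 (all SAEs) and a narrower one afterwards (fatal or vaccine-related). Section 9.6.2 defines incidence over participants with follow-up in the relevant period. If that period is the whole study, the denominator implies ascertainment that the protocol does not require.

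SAEs are a primary safety endpoint, and safety to Month 30 is a stated aim of Period II. A report that follows the plan literally would label a percentage and exact CI as whole-study all-cause SAE incidence. Non-fatal SAEs judged unrelated would be missing from most of Period II, so the figure could only understate the true one.

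**Working it through.** **The plan's own SAE figure.** Section 9.9 says that zero SAEs among 100 participants gives 95% confidence that the rate is below 3.0%. The one-sided exact bound is 1 − 0.05^(1/100) = 2.95%, so the figure is reproduced. (The two-sided Clopper-Pearson bound, 1 − 0.025^(1/100) = 3.62%, would not match.) The sentence is correct but states no time window.

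**Inputs**

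- 1 month = 30 days, 1 week = 7 days (Schedule of Activities, Section 1.3).
- Last dose, all arms: Month 6 ± 4 weeks (Sections 1.3 and 8.1.9.1), so L = 180 ± 28 = day 152 to 208.
- All-cause SAE window: 6 months after the last dose (Sections 4.1 and 8.4.1) = 180 days.
- Month 7 visit: 3 to 7 weeks after the Month 6 dose (Section 1.3), so d = 21 to 49 days; nominally day 210.
- Month 30 visit: ± 4 weeks (Section 1.3), so M30 = 900 ± 28 = day 872 to 928.

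**End of all-cause collection** = L + 180

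- Nominal: 180 + 180 = day 360 (Month 12).
- Range: 152 + 180 = day 332 to 208 + 180 = day 388 (11.1 to 12.9 months).

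**Length of the gap** = M30 − (L + 180)

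- Nominal: 900 − 360 = 540 days (18 months).
- Range: 872 − 388 = 484 to 928 − 332 = 596 days (16.1 to 19.9 months).

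**Share of the whole study outside all-cause collection** = gap / M30

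- Nominal: 540/900 = 60%.
- Range: 484/872 = 55.5% to 596/928 = 64.2%.
- With the Table 6 serum target of day 913 for Month 30: (913 − 360)/913 = 553/913 = 60.6%.

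**Share of Period II outside all-cause collection** = 1 − (180 − d)/(M30 − L − d)

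- Nominal: Period II is 900 − 210 = 690 days, of which 360 − 210 = 150 are covered and 540/690 = 78.3% are not.
- Minimum (d = 21, L = 208, M30 = 872): 1 − 159/643 = 75.3%.
- Maximum (d = 49, L = 152, M30 = 928): 1 − 131/727 = 82.0%.

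**Could another provision close the gap?**

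- *New medical conditions* are recorded throughout, but Sections 4.1 and 8.1.4 define them as events not considered SAEs.
- *AE monitoring* is scheduled at Months 18 and 30 in Section 1.3, but that does not override the explicit 6-month limit in Section 8.4.1.
- *Table 4* does not define its protocol-specified follow-up period. Its separate provision for deaths up to study completion makes sense only if the report-all period ends earlier.

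**Does Month 12 apply to those counted in the row?** Participants with fewer doses reach the 6-month limit sooner. Section 9.5.2 says that for one-dose participants, and for 3-dose-arm participants whose two doses do not match the 0, 6 regimen, "a safety profile listing will be created separately from the safety reports". Month 12 therefore applies in general to participants in the arm summaries.

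**The case against.** The strongest reply is that an SAE *observed* during the study can mean one reported under the collection rules, which Sections 4.1 and 8.4.1 spell out. The plan never calls the row a 30-month all-cause incidence, so all that is missing is a footnote. This does not remove the fault. On that reading one percentage and one CI still mix full capture to about Month 12 with fatal-or-related capture afterwards, and nothing tells the reader so.

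Some narrower points stand:

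- Deaths are SAEs and are collected whatever the cause to study completion, so the gap concerns only non-fatal SAEs judged unrelated. For these, reporting is no longer *required*; some may still be entered.
- Table 8 does not say which period its CI belongs to. That the CI extends to the whole-study column rests on the absence of any restriction.
- The 60% and 78% measure calendar time, not bias. Table 8 is cumulative, so the Period II share shows how little of that period is covered; it does not describe a separate planned summary.
- The ranges assume visits within window, and the safety population sets no such limit.
- The study is estimation-only, with no comparison between arms, so no test, error rate or sample size is affected.

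Limiting all-cause collection to 6 months may well be deliberate. The point does not dispute that choice; it asks only that the summary state the same window.

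**Conclusion.** The concern holds. The current text defines the all-cause SAE summary over a period about 18 months longer than the period in which such events must be reported. The uncovered part is about 60% of the study and 78% of Period II, assuming 30-day months, in-window visits and a complete regimen. The fault is in the stated window of the summary, not in SAE collection or the exact binomial method. No number of affected SAEs is given, because that needs a background rate the documents do not supply. This should be fixed before final database lock, because following the plan as written would mislabel a primary safety result.

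**What to change.** - In Section 9.4.2 and the Table 8 Serious AEs row, define the longer all-cause SAE summary and its 95% CI as running from Day 1 to 6 months after the last dose.
- Keep the whole-study window for deaths and serious vaccine-related AEs, so that later events of those kinds still appear in their own rows.
- Leave the Day 1 to 15 SAE summary and the Month 7 cut for the girls' base-phase report as they are.
- Optionally, add the same window to the zero-SAE sentence in Section 9.9. The figure does not change.

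The cost is one bullet, one table row or footnote and, if wanted, one clause. Section 9 allows such changes in the supplemental SAP before final database lock. Visits, data collection, SAE reporting and the definitions used by sites are untouched.
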